## 4. PATIENT ELIGIBILITY CRITERIA

This study can fulfill its objectives only if appropriate patients are enrolled. The following eligibility criteria are designed to select patients for whom participation in the study is considered appropriate. All relevant medical and nonmedical conditions should be taken into consideration when deciding whether a particular patient is suitable for this protocol.

### 4.1. Inclusion Criteria

Patients must meet all of the following inclusion criteria to be eligible for enrollment in the study:

1. Histological diagnosis of locally advanced (primary or recurrent) or metastatic solid tumors treated as follows (See [Table 1](#) for cohorts):
  - a. NSCLC monotherapy (Cohort 1):
    - Disease progression (PD) on 1st-line monotherapy anti-PD-1/-L1.
  - b. NSCLC combination (Cohort 2):
    - PD on 1st-line anti-PD-1/-L1 plus standard doublet platinum-containing regimen; or
    - PD on 1st-line anti-PD-1/-L1 plus standard doublet platinum-containing regimen followed by continuation of single agent anti-PD-1/-L1).
  - c. Renal cell carcinoma (RCC) with clear cell component (Cohort 3):
    - PD on 2nd-line monotherapy anti-PD-1/-L1; or
    - PD on 1st-line combination of doublet anti-PD-1/-L1 with anti-CTLA-4; or
    - PD on 1st-line combination of avelumab with axitinib or pembrolizumab with axitinib.
  - d. HR+ HER2- adenocarcinoma of the breast (Cohort 4):
    - PD on 1st-line combination of doublet palbociclib with hormonal therapy.
  - e. Castrate-resistant adenocarcinoma of the prostate (Cohort 5):
    - PD on enzalutamide monotherapy.
  - f. Castrate-resistant adenocarcinoma of the prostate (Cohort 6):
    - PD on abiraterone in combination with prednisone.

g. germline mutated BRCA (gBRCAm), HER2- adenocarcinoma of the breast (Cohort 7):

- PD on a PARP inhibitor monotherapy in patients previously treated with chemotherapy in the neoadjuvant, adjuvant, or metastatic setting.

2. Radiographic evidence of PD, including the target lesion being subjected to biopsy for the study, on the most recent regimen that requires a change in anti-cancer treatment.
3. Medically stable for a biopsy procedure as defined by the local institutional guidelines.
4. A tumor lesion for the *de novo* biopsy that meets the following criteria:
  - a. Is safely accessible to a biopsy procedure (ie, core needle, excisional) performed in accordance with local institutional practice standards;
  - b. Is anticipated to yield an amount of tumor tissue sufficient to meet the objectives of the study (see [Section 2](#));
  - c. Not previously irradiated;
  - d. Does not require decalcification for subsequent processing. (ie, no bone lesions).
5. Availability and adequacy of an archival, formalin-fixed, paraffin embedded (FFPE) tumor tissue block confirmed during Screening as containing sufficient tumor tissue to allow for sectioning of up to 25 slides each containing tissue sections that are 5 microns thick with a minimum tissue cross-sectional area of approximately 5 mm^2 and containing a minimum of approximately 20-40% tumor by ratio of tumor nuclei to benign nuclei. Fewer slides may be required for FFPE tissue blocks containing tissue that is greater than 5 mm^2 in cross-sectional area or greater than 40% tumor. Where local or regional regulations prevent submission of the archival tumor tissue block, a designated number of unstained slides each containing the indicated minimum amount of tissue must be submitted (refer to the laboratory manual for the required number of slides based on cross sectional area of tissue available in the FFPE tissue block) (See [Section 5.1.3](#)).
6. Post-progression biospecimen collection can be performed within 45 days of obtaining informed consent for the study.
7. Post-progression biospecimen collection can be performed within 45 days of the last dose of the most recent anti-cancer regimen.
8. Age  $\geq$ 18 years at the time of informed consent.
9. Patients who are willing and able to comply with scheduled visits and study procedures.

10. Evidence of a personally signed and dated informed consent document indicating that the patient has been informed of all pertinent aspects of the study.

#### **4.2. Exclusion Criteria**

Patients with any of the following characteristics/conditions will not be included in the study:

1. Discontinuation of current or most recent anti-cancer therapy due to toxicity and not progressive disease.
2. Initiation of new anti-cancer therapy after PD prior to planned biopsy.
3. Any medical condition that, in the investigator's judgement, unacceptably increases risk associated with the tumor biopsy or blood sampling procedures (eg, evidence of inadequate wound healing, significant neutropenia or thrombocytopenia, recent history of clinically significant bleeding or tumor hemorrhage).
4. Cohorts 1, 2 and 3 (NSCLC monotherapy, NSCLC combination, RCC with clear cell component) only: Treatment with an anti-PD-1/-L1 agent prior to current or most recent anti-PD-1/-L1 therapy.
5. Cohort 4 (HR+ HER2- breast cancer) only: Treatment with a CDK 4/6 inhibitor prior to current or most recent CDK 4/6 inhibitor.
6. Cohort 5 (castrate-resistant prostate cancer) only: Treatment with an agent that blocks adrenal androgen synthesis (eg, abiraterone acetate) and a second-generation AR antagonist other than enzalutamide (eg, apalutamide).
7. Patients who are investigator site staff members directly involved in the conduct of the study and their family members, site staff members otherwise supervised by the investigator, or patients who are Pfizer employees, including their family members, directly involved in the conduct of the study.
8. Other acute or chronic medical or psychiatric condition including recent (within the past year) or active suicidal ideation or behavior or laboratory abnormality that may increase the risk associated with study participation or may interfere with the interpretation of study results and, in the judgment of the Investigator, would make the patient inappropriate for entry into this study.
9. Austria only: Pregnant female patients; breastfeeding female patients.

## 5. STUDY PROCEDURES

### 5.1. Screening (Study Day -45 to Day 1)

#### 5.1.1. Informed Consent

Informed Consent will be obtained prior to any study-related activities. Consent should be obtained as close as possible to the day of the biospecimen collection, optimally the day of, but within 45 days before the *de novo* biopsy or research blood collection (whichever is sooner).

#### 5.1.2. Preliminary Eligibility Assessment

Prior to progressing to archival tumor tissue assessment, a preliminary eligibility assessment should be made by confirming the following:

- Demographics (Inclusion Criterion 8);
- Histological diagnosis of locally advanced or metastatic solid tumors and most recent standard of care anti-cancer therapy (Inclusion Criterion 1);
- Prior systemic anti-cancer therapy regimens or radiation therapy (Inclusion Criteria 1, 4c);
- New anti-cancer therapy which has not already been started (Exclusion Criterion 2);
- Reasons for discontinuation of current or most recent anti-cancer therapy (Exclusion Criterion 1).

Patients who have started new anti-cancer therapy **prior** to performing the *de novo* tumor tissue biopsy or research blood collection are not eligible and should be discontinued.

Screen failures are defined as participants who consent to participate in the clinical study but do not subsequently undergo biospecimen collection (ie, *de novo* tumor biopsy and research blood collection are not performed).

Patients *are permitted* to participate in interventional treatment clinical trials at the same time as participating in Study A9001502, with prior Sponsor agreement.

#### **5.1.4. Confirmation of Eligibility**

Prior to Enrollment, medical and oncological history should be reviewed to confirm if there have been any changes to systemic anti-cancer therapy regimens or radiation therapy or reasons for treatment discontinuation.

Radiographic evidence of PD for the lesion being targeted for the *de novo* tumor tissue biopsy must also be confirmed.

**The patient should be discontinued and should not undergo further study-related activities (including *de novo* tumor tissue biopsy or research blood collection) if new anti-cancer therapy has already been started following disease progression.** The participant should be recorded as a screen failure in the case report form (CRF).

#### **5.1.5. Re-Screening**

Re-screening is permitted on a case-by-case basis and only with prior agreement from the study Sponsor.

### **5.2. Enrollment (Study Day 1)**

Following confirmation of eligibility, the patient may be enrolled in the study and undergo study-related procedures.

### **5.2.1. Biospecimen Collection**

Biospecimen collection may occur on different days; however, *de novo* tumor biopsy or research blood collection must occur within 45 days of obtaining study Informed Consent.

Day 1 of the study is the date on which the *de novo* tumor biopsy or research blood collection occurs (whichever is sooner, if occurring on different dates). Research blood collection must occur  $\leq$ 5 days before, or  $\leq$ 1 day (24 hours) after, the *de novo* biopsy.

#### **5.2.1.1. Archival Tumor Tissue Submission**

Eligible archival FFPE tumor tissue (or equivalent) from the most recent primary or metastatic tumor biopsy or resection (see [Section 5.1.3](#)) should be submitted for analyses. Please refer to the laboratory manual for detailed collection, processing, storage, and shipment instructions.

All submitted FFPE tissue blocks (or equivalent slides) will be returned as soon as possible after the required number of sections are obtained and analyzed.

#### **5.2.1.2. *De Novo* Tumor Biopsy**

Performing a *de novo* biopsy should be compatible with the overall patient treatment plan. Pre-biopsy clinical and laboratory assessments per institutional guidelines must be completed and reviewed prior to biopsy procedure. It is expected that these pre-biopsy assessments include but are not limited to hematology and coagulation profiles. Safe values for biopsy are per institutional standard operational procedures (SOP) and normal lab ranges. Anti-coagulation therapy needs to be held prior to the biopsy according to institutional guidelines.

*De novo* tumor biopsies (ie, core needle, excisional) should be conducted according to institutional guidelines. For core biopsies, a minimum 18 gauge core needle and 4 separate cores are recommended to ensure, to the greatest extent possible, that the quality and amount of tumor tissue obtained is sufficient to enable the intended sample analyses. Tumor tissue from cytologic sampling (eg, fine needle aspiration, pleural effusion, including FFPE cell pellet material) is not adequate and should not be submitted.

The *de novo* tumor biopsy should be processed locally by formalin fixation and paraffin embedding, following specific processing guidelines described in the laboratory manual. The resulting FFPE tissue block should be shipped in its entirety as part of the tumor tissue specimen collection kit (room temperature).

Any remaining post-progression biopsy material that is not used for molecular analyses as part of the study will be returned to the site where the biopsy was conducted within approximately 6 months of collection.

The post-progression *de novo* biopsy must be obtained within 45 days of the last dose of SOC treatment but prior to initiation of any subsequent anti-cancer therapy.

Post-progression *de novo* biopsy specimens must be shipped as soon as possible after the appropriate processing but no later than 2 weeks after collection to facilitate timely return of Next Generation Sequencing analyses. Please refer to the laboratory manual for detailed collection, processing, storage, and shipment instructions.

There will be no banking of tumor biopsy samples.

### **5.2.1.3. Research Blood Specimens**

Research blood specimens will be drawn into separate blood collection tubes as follows:

- a. Three 10-mL tubes of blood will be collected in specially provided tubes containing blood stabilizer (ie, Streck tubes, room temperature) for cfDNA analysis using a NGS panel approach.
- b. One 8.5-mL blood specimen will be collected in a specially provided tube containing blood stabilizer (eg, Paxgene blood DNA tube; Streck tube) for germline DNA sequence analysis. Results will be used as a control to compare with tumor DNA sequence results in order to identify tumor-specific (ie, somatic) gene alterations, and/or to investigate the potential contribution of specific gene alterations to mechanisms of resistance. Remaining DNA material may also be used for translational analyses as indicated below (item c).
- c. One 8.5 mL blood specimen will be collected in a specially provided tube containing blood stabilizer (eg, Paxgene blood DNA tube; Streck tube) for additional translational analyses which may include, but may not be limited to, T and/or B cell receptor sequence analysis or epigenetic profiling by NGS.

Research blood collection may be performed at a separate visit (which may be a home visit, if appropriate) to the *de novo* tumor tissue biopsy but **must occur  $\leq$ 5 days before or  $\leq$ 1 day (24 hours) after the *de novo* biopsy**.

The post-progression research blood specimens must be obtained within 45 days of the last dose of SOC treatment and prior to initiation of any subsequent anti-cancer therapy.

The research blood specimens must be **shipped no later than one week after collection**. Please refer to the laboratory manual for detailed collection, processing, storage, and shipment instructions.

There will be no banking of blood samples.

### **5.2.2. Additional Medical and Oncological History**

Smoking history, prior surgery, duration and best overall response for each therapy should be recorded in the CRF.

### **5.2.3. Pregnancy Testing (*Specific to Austria*)**

Monthly pregnancy tests will be performed per institutional guidelines.

### **5.3. Post-Biospecimen Collection Follow-Up ( $\leq 30$ days after receipt of NGS results at the provider's facility)**

#### **5.3.1. NGS Results Consultation**

NGS results will be reviewed at a post-biospecimen follow-up consultation visit, which should occur within 30 days of receipt of the *de novo* tumor biopsy or cfDNA NGS results at the provider's facility. These visits should be conducted in-person; however, phone visits are permitted if the patient is unable or unwilling to travel to the facility.

CCI

[figure not shown]
CCI

CCI

CCI

#### **5.3.3. Next Anti-Cancer Therapy**

The patient's next anti-cancer therapy following *de novo tumor* biopsy or cfDNA sample collection, and whether it was impacted by the NGS results, will be recorded in the case report form (CRF).

### **5.4. Patient Withdrawal**

Patients may withdraw from the study at any time at their own request, or they may be withdrawn at the discretion of the Investigator or Sponsor for safety or behavioral reasons, or the inability of the patient to comply with the protocol-required schedule of study visits or procedures.

Reasons for withdrawal from the study may include:

- Study terminated by Sponsor;
- Lost to follow-up;
- Refused further follow-up;
- Death.

If the patient withdraws from the study, and also withdraws consent for disclosure of future information, no further procedures, visits or assessments should be performed, and no additional data should be collected. The sponsor may retain and continue to use any data collected before such withdrawal of consent.

**Withdrawal of consent:**

Patients should notify the investigator in writing of the decision to withdraw consent from post-biospecimen follow-up, whenever possible. The withdrawal of consent should be explained in detail in the medical records by the investigator, as to the reason and entered on the appropriate case report form (CRF) page.

**Lost to follow-up:**

All reasonable efforts must be made to locate patients to determine post-biospecimen follow-up. Lost to follow-up is defined by the inability to reach the patient after a minimum of 2 documented phone calls, faxes, or e-mails as well as lack of response by the patient to 1 registered mail letter. All attempts should be documented in the patient's medical records.

**6. ASSESSMENTS**

Every effort should be made to ensure that the protocol-required procedures, visits and assessments are completed as described. However, it is anticipated that from time to time there may be circumstances, outside of the control of the Investigator that may make it unfeasible to perform the procedure(s), visits or assessments within the designated times. In these cases, the Investigator will take all steps necessary to ensure the safety and well-being of the patient. The study team will be informed of these incidents in a timely fashion.

For samples being collected and shipped, detailed collection, processing, storage, and shipment instructions and contact information will be provided to the investigator site prior to initiation of the study in the study laboratory manual.

Patients should follow the approved package insert for any ongoing medications.

CCI  
[REDACTED]CCI  
[REDACTED]CCI  
[REDACTED]CCI  
[REDACTED]CCI  
[REDACTED]CCI  
[REDACTED]CCI  
[REDACTED]CCI  
[REDACTED]CCI  
[REDACTED]CCI  
[REDACTED]

### **6.3. Pregnancy Testing (*Specific to Austria*)**

Pregnancy tests will be performed at the times listed in the [Schedule of Activities](#).

Pregnancy tests may also be repeated if requested by institutional review boards (IRBs)/ethics committees (ECs) or if required by local regulations.

## **7. SAFETY**

### **7.1. Adverse Events**

An AE is defined as any untoward medical occurrence and can therefore be any unfavorable and unintended sign (including an abnormal laboratory finding), symptom, or disease, whether or not related to the patient's participation in the study.

Any AE that occurs from the time the patient undergoes the tumor biopsy and research blood collection, whichever occurs first, through and including 24 hours post tumor biopsy and blood collection must be recorded. The investigator is required to assess whether the AE may be related to the patient's participation in the study.

The investigator must pursue and obtain information adequate to determine the outcome of the AE and to assess whether it meets the criteria for classification as a research related injury requiring immediate notification to Pfizer as described below.

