3. **Archival tumor tissue assessment:** The archival tumor tissue from the most recent primary or metastatic tumor biopsy or resection is checked to confirm availability and adequacy of sample. See protocol [Section 5.1.3](#). If the archival tumor tissue does not meet protocol requirements, the patient must be discontinued and should not proceed with any further enrolment activities; the participant is recorded as a screen failure.
4. **Confirmation of Eligibility:** Confirmation of any changes to systemic anti-cancer therapy regimens, radiation therapy or reasons for treatment discontinuation; confirmation of radiographic evidence of disease progression for the lesion being targeted for the *de novo* tumor tissue biopsy.
5. **Additional medical and oncological history:** Following Enrollment, smoking history, prior cancer surgery, duration and best overall response for each anti-cancer therapy is recorded.
6. **Archival tumor tissue submission:** If the archival tumor tissue is confirmed as meeting protocol requirements ([Section 5.1.3](#)), the patient may be considered for enrollment. The archival tumor tissue must be processed and sent to the Central Laboratory as detailed in the laboratory manual.
7. ***De novo* tumor biopsy:** Occurs only if archival tumor tissue meets protocol requirements (see [Section 5.1.3](#)). *De novo* biopsy is performed according to institutional guidelines. Pre-biopsy clinical and laboratory assessments per institutional guidelines must be completed and reviewed prior to biopsy procedure. Anti-coagulation therapy needs to be held prior to the biopsy according to institutional guidelines. The biopsy must be performed  $\leq$ 45 days after the last dose of standard of care (SOC) treatment. Post progression *de novo* biopsy specimens must be shipped no later than 2 weeks after collection. Please refer to [Section 5.2.1.2](#) and the laboratory manual for detailed instructions.

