8. **Research blood collection:** Research blood collection may be performed at a separate visit (which may be a home visit, if appropriate) to the *de novo* tumor tissue biopsy but must occur  $\leq$ 5 days before or  $\leq$ 1 day (24 hours) after the *de novo* biopsy. Please refer to the laboratory manual for detailed instructions. See [Section 8](#) for details. Research blood specimens must be shipped no later than one week after collection. Please refer to the laboratory manual for detailed collection, processing, storage, and shipment instructions.
9. **Pregnancy Test:** Specific only to Austria. Monthly pregnancy tests per institutional guidelines.
10. **Adverse event monitoring:** Adverse event collection will begin at the time of the *de novo* tumor biopsy and research blood collection, whichever occurs first, through and including 24 hours post-biospecimen collection.
11. **NGS results consultation:** NGS consultation will occur within 30 days of receipt of the *de novo* tumor biopsy or cfDNA NGS results at the provider's facility. These visits should preferably be conducted in person, although phone visits are permitted if the patient is unable or unwilling to travel to the facility.

CCI

CCI

14. **Next anti-cancer therapy decision:** Next anti-cancer medication following *de novo* tumor biopsy or cfDNA sample collection and whether impacted by the NGS results will be recorded in the appropriate CRF page.

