## 1.2. Potential Risks and Possible Benefits

The primary potential risk to patients who participate in the study is associated with the *de novo* tumor biopsy performed as a study-related procedure. To be eligible for the study patients must have a tumor lesion that is considered to be safely accessible to a *de novo* biopsy performed in accord with local institutional practice standards. See [Section 4](#) for details.

Possible benefits for patients who participate in the study derive from the NGS results from the analysis of their tumor tissue and/or blood performed by a third-party laboratory. These results are returned to the patient's physician/ health care provider who will then discuss the results with the patient. To enable sufficient time to thoroughly discuss the results and possible treatment implications, the study also supports the direct interaction between the patient and the physician by incorporating dedicated consultation time (See [Schedule of Activities](#)). Further, patients will be able to obtain a personal copy of the NGS results through their health care provider. It is recognized that results from NGS analysis of the patient's tumor tissue and/or blood may not directly impact the subsequent treatment plan. However, only by performing such analyses can low probability treatment opportunities be identified.

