#### **7.1.1. Research Related Injury**

Should a patient, in the investigator's opinion, suffer a medically important research related injury caused by their participation in the study, the designated Pfizer clinician or medical monitor must be notified immediately by emailing [CCI](#) [REDACTED]

A medically important research related injury is any untoward medical occurrence that:

- Results in death;
- Is life-threatening (immediate risk of death);
- Requires inpatient hospitalization or prolongation of existing hospitalization;
- Results in persistent or significant disability/incapacity (substantial disruption of the ability to conduct normal life functions);
- Results in congenital anomaly/birth defect.

Medical and scientific judgment is exercised in determining whether an injury is an important medical event. An important medical event may not be immediately life-threatening and/or result in death or hospitalization. However, if it is determined that the event may jeopardize the patient or may require intervention to prevent one of the other outcomes listed in the definition above, the important medical event should be reported as a research related injury.

An investigator may be requested by the designated Pfizer clinician or medical monitor to obtain specific additional follow-up information in an expedited fashion. In general, this will include a description of the injury in sufficient detail to allow for a complete medical assessment of the case and independent determination of possible causality. Information on other possible causes of the event, such as concomitant treatments, vaccines, and/or illnesses must be provided. In the case of a patient death, a summary of available autopsy findings must be submitted as soon as possible to Pfizer or its designated representative.

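### Adverse events during the anticoagulation hold before the study biopsy need not be recorded, and are absent from the AE summary if biopsy and blood draw are both cancelled

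*Protocol*

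**What the plan says.** Protocol Section 1.2 places the study's main risk in the "tumor biopsy performed as a study-related procedure". For that biopsy, Schedule of Activities footnote 7 states: "Anti-coagulation therapy needs to be held prior to the biopsy according to institutional guidelines". Section 5.2.1.2 repeats the sentence. How and for how long to hold is left to the institution; that it be held is a protocol requirement.

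The AE window is given twice. Section 7.1 covers "Any AE that occurs from the time the patient undergoes the tumor biopsy and research blood collection, whichever occurs first", and closes 24 hours after biopsy and blood collection. Footnote 10 starts collection at the "tumor biopsy and research blood collection, whichever occurs first, through and including 24 hours post-biospecimen collection". In the Schedule, the AE row is marked under Biospecimen Collection and under Follow-up; there is no mark under Screening. Section 5.2.1 sets Day 1 as the date on which the biopsy or "research blood collection occurs (whichever is sooner, if occurring on different dates").

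The blood draw can come ahead of the biopsy. Footnote 8 says: "Research blood collection may be performed at a separate visit (which may be a home visit, if appropriate"), from 5 days before to 24 hours after the biopsy.

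Two other duties bear on the point. Section 7.1.1 requires immediate notification to the sponsor if a patient should, in the investigator's opinion, "suffer a medically important research related injury caused by their participation in the study". Section 6 deals with circumstances outside the investigator's control that make a procedure unfeasible, and adds: "The study team will be informed of these incidents in a timely fashion".

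On analysis, Section 5.1.2 classes a consented patient with no biospecimen collection as a screen failure. SAP 5.1 limits the Safety Analysis (SA) population to enrolled patients who had a biopsy or a research blood draw. SAP 8.3 provides descriptive AE statistics in that population.

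**The concern.** Stopping an anticoagulant carries a risk of its own, separate from the needle. Here it is stopped because the study asks for a biopsy, so any harm during the hold is harm from a step that the protocol requires. A hold comes before the biopsy by nature, whereas mandatory AE recording starts at the biopsy or at a blood draw. The window can therefore miss the part of the preparation in which such harm would arise.

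The case that stands out is an event that stops the study for that patient. If neither biopsy nor blood draw takes place, recording never becomes mandatory and the patient is not in the population that the AE summary describes. What is at stake is the completeness of the descriptive account of procedure-related harm. The primary endpoint, a paired comparison of gene-alteration frequencies, is not touched.

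**Working it through.** No figure in the plan is in dispute and no arithmetic applies. The check sets the texts side by side and follows a held patient through the possible orders of events.

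**Can such patients be enrolled?** The visible criteria in Sections 4.1 and 4.2 do not exclude patients on anticoagulants, and footnote 7 expects them. Consent must precede study-related activities and may be given up to 45 days before collection (Section 5.1.1). A hold made for the study biopsy therefore fits between consent and Day 1.

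**Where does the hold fall?** Day 1 is the date of the first procedure, so any part of the hold before that date lies in Screening, where the Schedule has no AE entry.

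**What happens to an event during the hold?**

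| Course of events | Must it be recorded as an AE under Section 7.1? | Is the patient in the SA population? |
|---|---|---|
| Biopsy first, or blood drawn at the same visit | No, for the hold before that first procedure | Yes |
| Blood drawn up to 5 days before the biopsy | No before the draw; yes once the draw opens the window | Yes |
| Blood drawn, biopsy then cancelled | No before the draw; the draw opens the window | Yes |
| Both procedures cancelled | No, the window never opens | No, screen failure |

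An early blood draw narrows the gap, but it is optional.

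**What does Section 7.1.1 recover?** It states no start time. Its list covers death, threat to life, hospitalization, lasting disability and congenital anomaly. It also extends to events that put the patient at risk or call for treatment to avert one of those outcomes. A clinically important clot during a hold would qualify if the investigator attributed it to participation. Lesser events would not.

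**What does Section 6 recover?** The study team learns that a procedure could not be done. No AE record is required, and the duty does not arise when the biopsy goes ahead after a lesser event.

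**What does SAP 8.3 exclude?** It sets no limit on onset date. For a patient who later has a procedure, an event in the hold that was recorded anyway is not shut out of the summary; the protocol simply does not require the record. Exclusion is certain only in the last row of the table.

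**The case against.** The strongest reply is that the events that matter are already caught. Section 7.1.1 has no start time and is broader than a list of serious outcomes, so an important event attributed to the hold should reach the sponsor at once. Risk is also screened beforehand: Inclusion Criterion 3 asks for medical stability for biopsy, Exclusion Criteria 3 and 8 remove patients at undue risk, and Section 5.2.1.2 requires pre-biopsy assessments to be reviewed. The study has no investigational product (Appendix 4), no formal safety analysis (Section 8.4) and no visible safety endpoint. Starting AE collection at the procedure is a coherent choice in such a study. CRF completion instructions, which might settle practice at sites, are not among the documents.

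Most of this stands, and it is why the point is minor. It does not close the gap entirely. Notification under Section 7.1.1 does not put a screen failure into the AE summary, and it does not reach lesser events. Because that section follows one whose recording window opens at the first procedure, a site could also reasonably doubt that it applies during Screening.

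A reader might go further and infer that serious hold-related events go unreported, or that no such event can enter the AE summary. The documents support neither. The first overlooks Section 7.1.1. The second overlooks that SAP 8.3 has no onset limit and that Section 7.1 says what must be recorded without forbidding more.

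**Conclusion.** The point holds in limited form, at minor severity. Following the plan exactly, events in the part of the hold before the first procedure need not be recorded as AEs. After allowing for Section 7.1.1, two things remain: lesser events, for which no record is required, and any event in a patient in whom both procedures are cancelled, which is certain to be absent from the SAP 8.3 summary.

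The size cannot be estimated. The share of patients on anticoagulants, the length of the hold and the event rate are all missing from the documents, so neither a count nor a rate of missed events can be given. The conclusion assumes that the hold is made for the study biopsy and begins after consent; a hold started earlier in usual care is a different matter. It also assumes that sites record what the protocol requires and no more.

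**What to change.** Leave the conduct of the hold to institutional guidelines and change the reporting text in two places.

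1. In footnote 10 and Section 7.1, add that AEs which the investigator relates to study-required biopsy preparation, including an anticoagulation hold, are recorded from informed consent onward. State that Section 7.1.1 applies from consent as well.
2. In SAP 8.3, add a listing of these events for all consented patients, including screen failures. The SA population and its AE summary stay as they are.

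This does not open AE collection to everything that happens in Screening, and it needs no hold-start date on the CRF. It adds no visit or procedure. The cost is the wording, one listing and a few extra AE records, some of them for patients who are never biopsied. Section 5.1.4 already has one kind of screen failure entered in the CRF, so a record for such patients has a precedent.
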